11 COLLABORATIVE AGREEMENTS

11.1 COOPERATIVE RESEARCH AND DEVELOPMENT AGREEMENT (CRADA)

11.1.1 BlueLink (CRADA #03049)

The investigational study agent formerly named CRLX101 was being provided by the company, BlueLink under a Collaborative Agreement [Cooperative Research and Development Agreement (CRADA)].

As of March 2020, the CRADA has been amended to switch the manufacturer from BlueLink to Ellipses and drug name from CRLX101 to EP0057.

11.1.2 Astra Zeneca (CRADA #02299)

The investigational study agent, olaparib is provided by the company, Astra Zeneca under a Collaborative Agreement [Cooperative Research and Development Agreement (CRADA)].

12 HUMAN SUBJECTS PROTECTIONS

12.1 RATIONALE FOR SUBJECT SELECTION

As previously described, the subjects for this study will include all subjects who meet the eligibility criteria outlined in section [2.1](#). No gender, racial, or ethnic groups will be excluded from participation in this trial.

The effects of EP0057 and olaparib on the developing human fetus are unknown. For this reason, participants will be required to use contraception

12.2 PARTICIPATION OF CHILDREN

Because no dosing adverse event data are currently available on the use of EP0057 in combination with olaparib in subjects <18 years of age, children are excluded from this study.

12.3 EVALUATION OF BENEFITS AND RISKS/DISCOMFORTS

12.3.1 Risks

12.3.1.1 Study drug risks

The risks associated with the specific study agents are described in sections [14.1.9](#) and [14.2.9](#). Subjects will be adequately monitored for the occurrence of any possible side effects.

12.3.1.2 Biopsy risks

The risks associated with biopsies are pain and bleeding at the biopsy site. In order to minimize pain, local anesthesia will be used. Rarely, there is a risk of infection at the sampling site. CT guidance may be used in obtaining biopsies.

12.3.1.3 Conscious sedation risks

There is a possibility that conscious sedation may be used for the procedure. The common side effects of conscious sedation include drowsiness, delayed reflexes, hypotension, headache, and nausea. These are generally mild and last no more than a few hours.

12.3.1.4 Radiation risks

Subjects will be exposed to radiation from 3 CT guided biopsies and up to 9 CTs. The amount of radiation exposure is equal to approximately up to 12.3 rem.

Note: As accrual to cohort 4 (mCRPC) ended with amendment version 7/27/2021, CT c/a/p and bone scan every 3 weeks are not included in the calculated radiation dose above.

12.3.1.5 Risks from CT scans

There is a chance of developing an allergic reaction from the contrast material, which may cause symptoms ranging from mild itching or a rash to severe difficulty breathing, shock or rarely, death. The contrast material may also cause kidney problems. Patients may feel discomfort when the contrast material is injected.

12.3.1.6 Risks related to blood sampling

Side effects of blood draws include pain and bruising, lightheadedness, and rarely, fainting. Up to 225 mL of blood may be drawn at any given visit, with a maximum of 529 mL in an 8-week period.

12.3.1.7 Risk related to hair collection

The only risk associate with hair collection is pain.

12.3.2 Benefits

The benefits include a possible decrease in the size of the tumor and the scientific knowledge that could be acquired through this trial.

12.4 CONSENT PROCESS AND DOCUMENTATION

The informed consent document will be provided as a physical or electronic document to the participant for review prior to consenting. A designated study investigator will carefully explain the procedures and tests involved in this study, and the associated risks, discomforts and benefits. In order to minimize potential coercion, as much time as is needed to review the document will be given, including an opportunity to discuss it with friends, family members and/or other advisors, and to ask questions of any designated study investigator. A signed informed consent document will be obtained prior to entry onto the study.

The initial consent process as well as re-consent, when required, may take place in person or remotely (e.g., via telephone or other NIH approved remote platforms used in compliance with policy, including HRPP Policy 303) per discretion of the designated study investigator and with the agreement of the participant. Whether in person or remote, the privacy of the subject will be

maintained. Consenting investigators (and participant, when in person) will be located in a private area (e.g., clinic consult room). When consent is conducted remotely, the participant will be informed of the private nature of the discussion and will be encouraged to relocate to a more private setting if needed.

Consent will be documented with required signatures on the physical document (which includes the printout of an electronic document sent to participant) or as described below, with a manual (non-electronic signature) on the electronic document. When required, witness signature will be obtained similarly as described for the investigator and participant.

Manual (non-electronic) signature on electronic document:

When a manual signature on an electronic document is used for the documentation of consent at the NIH Clinical Center, this study will use the following to obtain the required signatures:

- Adobe platform (which is not 21 CFR Part 11 compliant); or,
- iMedConsent platform (which is 21 CFR Part 11 compliant)

During the consent process, participants and investigators will view individual copies of the approved consent document on screens at their respective locations (if remote consent); the same screen may be used when in the same location, but is not required.

Both the investigator and the participant will sign the document using a finger, stylus or mouse.

Note: Refer to the CCR SOP PM-2, Obtaining and Documenting the Informed Consent Process for additional information (e.g., verification of participant identity when obtaining consent remotely) found <https://ccrod.cancer.gov/confluence/pages/viewpage.action?pageId=73203825>.

12.4.1 Request for Waiver of Consent for Screening Activities

Prior to the participant signing the consent for this study pre-screening activities listed in Section **2.3.1** may be performed.

We request a waiver of consent for these activities as they involve only minimal risk to the participants. A waiver will not adversely affect the rights and welfare of the participants given that the activities are only intended to determine suitability for screening for participation in research protocols. These activities could not practicably be carried out without the waiver as central recruiting services, utilized in the NIH Clinical Center, perform pre-screening activities for multiple studies and obtaining consent for each one is beyond their resources. The participants will be provided with additional pertinent information after participation as they will be informed whether or not they are eligible to sign a consent for additional screening.

13 REGULATORY AND OPERATIONAL CONSIDERATIONS

13.1 STUDY DISCONTINUATION AND CLOSURE

This study may be temporarily suspended or prematurely terminated if there is sufficient reasonable cause. Written notification, documenting the reason for study suspension or termination, will be provided by the suspending or terminating party to study participants, investigator, funding agency, the Investigational New Drug (IND) sponsor and regulatory authorities. If the study is prematurely terminated or suspended, the Principal Investigator (PI) will promptly inform study participants, the Institutional Review Board (IRB), and sponsor and

will provide the reason(s) for the termination or suspension. Study participants will be contacted, as applicable, and be informed of changes to study visit schedule.

Circumstances that may warrant termination or suspension include, but are not limited to:

- Determination of unexpected, significant, or unacceptable risk to participants
- Demonstration of efficacy that would warrant stopping
- Insufficient compliance to protocol requirements
- Data that are not sufficiently complete and/or evaluable
- Determination that the primary endpoint has been met
- Determination of futility

Study may resume once concerns about safety, protocol compliance, and data quality are addressed, and satisfy the sponsor, IRB and as applicable, Food and Drug Administration (FDA).

13.2 QUALITY ASSURANCE AND QUALITY CONTROL

The clinical site will perform internal quality management of study conduct, data and biological specimen collection, documentation and completion. An individualized quality management plan will be developed to describe the site's quality management.

Quality control (QC) procedures will be implemented beginning with the data entry system and data QC checks that will be run on the database will be generated. Any missing data or data anomalies will be communicated to the site(s) for clarification/resolution.

Following written Standard Operating Procedures (SOPs), the monitors will verify that the clinical trial is conducted and data are generated and biological specimens are collected, documented (recorded), and reported in compliance with the protocol, International Council for Harmonisation Good Clinical Practice (ICH GCP), and applicable regulatory requirements (e.g., Good Laboratory Practices (GLP), Good Manufacturing Practices (GMP)).

The investigational site will provide direct access to all trial related sites, source data/documents, and reports for the purpose of monitoring and auditing by the sponsor, and inspection by local and regulatory authorities.

13.3 CONFLICT OF INTEREST POLICY

The independence of this study from any actual or perceived influence, such as by the pharmaceutical industry, is critical. Therefore, any actual conflict of interest of persons who have a role in the design, conduct, analysis, publication, or any aspect of this trial will be disclosed and managed. Furthermore, persons who have a perceived conflict of interest will be required to have such conflicts managed in a way that is appropriate to their participation in the design and conduct of this trial. The study leadership in conjunction with the National Cancer Institute has established policies and procedures for all study group members to disclose all conflicts of interest and will establish a mechanism for the management of all reported dualities of interest.

13.4 CONFIDENTIALITY AND PRIVACY

Participant confidentiality and privacy is strictly held in trust by the participating investigators, their staff, and the sponsor(s). This confidentiality is extended to cover testing of biological samples and genetic tests in addition to the clinical information relating to participants.

Therefore, the study protocol, documentation, data, and all other information generated will be

held in strict confidence. No information concerning the study or the data will be released to any unauthorized third party without prior written approval of the sponsor.

All research activities will be conducted in as private a setting as possible.

The study monitor, other authorized representatives of the sponsor, representatives of the Institutional Review Board (IRB), and/or regulatory agencies may inspect all documents and records required to be maintained by the investigator, including but not limited to, medical records (office, clinic, or hospital) and pharmacy records for the participants in this study. The clinical study site will permit access to such records.

The study participant's contact information will be securely stored at the/each clinical site for internal use during the study. At the end of the study, all records will continue to be kept in a secure location for as long a period as dictated by the reviewing IRB, Institutional policies, or sponsor requirements.

Study participant research data, which is for purposes of statistical analysis and scientific reporting, will be stored at the NCI CCR. This will not include the participant's contact or identifying information. Rather, individual participants and their research data will be identified by a unique study identification number. The study data entry and study management systems used by the clinical site(s) and by NCI CCR research staff will be secured and password protected. At the end of the study, all study databases will be archived at the NIH.

To further protect the privacy of study participants, a Certificate of Confidentiality has been issued by the National Institutes of Health (NIH). This certificate protects identifiable research information from forced disclosure. It allows the investigator and others who have access to research records to refuse to disclose identifying information on research participation in any civil, criminal, administrative, legislative, or other proceeding, whether at the federal, state, or local level. By protecting researchers and institutions from being compelled to disclose information that would identify research participants, Certificates of Confidentiality help achieve the research objectives and promote participation in studies by helping assure confidentiality and privacy to participants.

14 PHARMACEUTICAL INFORMATION

14.1 EP0057 (IND#130102)

14.1.1 Description

EP0057 is a polymer drug conjugate composed of 20 (S)-camptothecin conjugated to a biocompatible polymer. The compound self assembles into soluble nanoparticles composed of several molecules when dissolved in aqueous solution. Camptothecin (CPT) is an antineoplastic that inhibits topoisomerase I resulting in cell death during the S phase of the cell cycle. EP0057 nanoparticles are believed to be taken up by tumor cells followed by release of the active pharmaceutical ingredient 20(S)-camptothecin.

14.1.2 Supplier/How Supplied

The EP0057 is provided by the company, Ellipses, the manufacturer of the drug under a Collaborative Agreement [Cooperative Research and Development Agreement (CRADA)].

EP0057 will be provided at no cost to the study patient. It is supplied as a lyophilized cake in 30 mL single-use vial containing 35 mg of CPT equivalents (approximately 350 mg of polymer drug conjugate).

14.1.3 Handling and Dispensing

EP0057 is a sterile injectable and must be handled under appropriate controls, conditions, and aseptic techniques to maintain product sterility. EP0057, a cytotoxic, should be prepared in a class II biological safety cabinet using standard precautions for the safe handling of antineoplastic agents. Latex gloves are recommended. It must be dispensed only from official study sites by authorized personnel according to local regulations, and stored in a secure area according to local regulations. It is the responsibility of the Investigator to ensure that study drug is only dispensed to eligible study patients.

14.1.4 Preparation

Vials of EP0057 should be removed from the refrigerator and warmed to room temperature for approximately one hour prior to preparation. Concentrated EP0057 solution is prepared by adding 14 mL of SWFI to each 35 mg vial. The required volume of SWFI is to be aseptically withdrawn into a sterile calibrated syringe and the syringe needle inserted through the vial septum. The SWFI should be slowly added along the inside of the vial wall and not directly onto the lyophilized product cake to minimize foaming. The product is dissolved by gentle swirling (do not shake) until a clear homogenous solution is achieved. The majority of the product cake will dissolve quickly, however complete dissolution to a clear, homogenous solution will take longer and may require up to 30 minutes. The EP0057 concentrated solution should be inspected visually for particulate matter prior to further preparation. Visually inspect for completion of reconstitution every 2-3 minutes. Reconstitution is complete when (i) foam head has dissipated down to a thin bubble ring along inner wall of vial, (ii) solids in solution and foam head are no longer visible, and (iii) translucent polymer “vapors” are no longer visible in solution and the solution is clear and uniform in appearance. Complete reconstitution of the vial may take up to 30 minutes.

Each milliliter of concentrated solution contains 2.5 mg of camptothecin equivalents. Concentrated EP0057 solution is diluted to the recommended dose with 5% dextrose in water for injection (D5W) to a total volume of 500 mL. After determining the amount of EP0057 concentrated solution required for dosing, an equivalent volume is aseptically withdrawn from a 500 mL infusion bag or bottle of D5W with a calibrated syringe. The measured volume of concentrated EP0057 solution is then withdrawn with a calibrated syringe and injected into the prepared 500 mL D5W infusion bag or bottle. The solution is thoroughly mixed by gentle manual rotation.

14.1.5 Storage and Stability

EP0057 vials should be stored at refrigerated conditions (2° - 8°C) and should only be accessible to authorized individuals. EP0057 is stable for at least 3 years when stored at refrigerated conditions (2° - 8°C). The reconstituted solution is stable for 24 hours when stored at room temperature. Any unused product solution from the reconstituted vials should be destroyed per the site's standard operating procedures.

Formulated EP0057 (i.e., IV bag) should be used within 6 hours of reconstituting the drug product vials.

14.1.6 Dosage and Administration

See Sections 3.2 and 3.3 for the dose levels and administration of EP0057 to be evaluated in this study.

See Section 3.3.4 for management of any EP0057 infusion related/hypersensitivity reactions.

The second and subsequent dose of EP0057 may be delayed if related AEs have not resolved to grade 1 or better. If a dose of EP0057 is delayed, then the subsequent dose should be administered 2 weeks later to avoid significant carry-over of unconjugated plasma CPT from one dose to the next (see Section 3.3). However, the maximum delay for AEs to resolve is 21 days beyond which the patient will be taken off treatment.

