3.3.2 Dosing Delays/Dose Modifications and Management of Toxicities

- In the case of toxicity, appropriate medical treatment should be used (including anti-emetics, anti-diarrheals, etc.).
- Once a patient has a dose reduction for toxicity, the dose will not be increased.
- A maximum of 2 dose reductions is permitted
- If either agent is discontinued due to toxicity, the patient may continue on the other agent.
- Participants continuing to experience toxicity at the off treatment visit will be contacted for additional assessments until the toxicity has resolved or is deemed irreversible. Patients must remain on the study to have additional assessment.
- For AEs that are unrelated to the study drugs, study drug may be held for up to 21 days at the discretion of the PI.
- The associate investigator and/or PI will determine whether one or both drugs are responsible for an observed toxicity and will manage that toxicity as described below.

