3.3.2.1 Hematologic toxicities

Table 8. Dose Modification and Management of Hematologic Adverse Events

Observation	Action
On day 1 and 15 Absolute neutrophil count (ANC) \geq 1500/mcL AND Platelets \geq 75,000/mcL AND Hemoglobin \geq 8 g/dL	No interruption.
On day 1 and 15 ANC $<$ 1500/mcL OR Platelets $<$ 75,000/mcL OR Hemoglobin $<$ 8 g/dL	If any weekly evaluation demonstrates grade \geq 3 neutropenia or grade \geq 2 thrombocytopenia, a repeat hematology assessment will be obtained 2-4 days later. On first occurrence , hold the drug(s) causing the toxicity for up to 21 days until ANC \geq 1500/mcL, platelets \geq 75,000/mcL, and hemoglobin \geq 9 g/dL. The associate investigator and/or PI will determine whether one or both drugs are responsible for an observed toxicity and will initiate appropriate medical therapy and no change in dose upon re-initiation. On second occurrence , hold the drug(s) causing the toxicity for up to 21 days until ANC \geq 1500/mcL, platelets \geq 75,000/mcL, and hemoglobin \geq 9 g/dL. Initiate appropriate medical therapy. Treatment with olaparib or EP0057 may be restarted at one dose level (DL) lower. Patients whose counts have not recovered to ANC \geq 1500/mcL, platelets \geq 75,000/mcL, and hemoglobin \geq 9 g/dL after 21 days should be removed from the drug causing the toxicity.
At any time during cycle Grade 4 hematologic AE	On first occurrence , hold the drug(s) causing the toxicity for up to 21 days until ANC \geq 1500/mcL, platelets \geq 75,000/mcL, and hemoglobin \geq 9 g/dL. Initiate appropriate medical therapy. Treatment with olaparib or EP0057 may be restarted at one DL lower. On second occurrence , discontinue the drug(s) causing the toxicity. Follow patient until

Table 8. Dose Modification and Management of Hematologic Adverse Events

Observation	Action
	resolution/stabilization of toxicity. Patients whose counts have not recovered to ANC \geq 1500/mcL, platelets \geq 75,000/mcL, and hemoglobin \geq 9 g/dL after 21 days should be removed from the drug causing the toxicity. See section 3.3.2.1 for exceptions.
Toxicities requiring more than 2 dose reductions	Remove patient from the drug causing the toxicity.

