- Treatment may be delayed for a maximum of 21 days after holding the treatment for toxicities that develop and do not resolve as defined above (the following AE's are exempt from hold: lymphopenia, or leukopenia in the absence of grade 3 or higher neutropenia).
- Weekly blood counts will be obtained during the first cycle, and then at day 1 and 15 of subsequent cycles.
- Management of prolonged hematological toxicities while on study treatment
 - If a patient develops prolonged hematological toxicity such as:
 - \geq 2 week interruption/delay in study treatment due to CTC grade 3 or worse anemia and/or development of blood transfusion dependence
 - \geq 3 week interruption/delay in study treatment due to CTC grade 3 or worse neutropenia (ANC $<$ 1,000/mcL)
 - \geq 3 week interruption/delay in study treatment due to CTC grade 3 or worse thrombocytopenia (Platelets $<$ 50,000/mcL)
 - Weekly differential blood counts including reticulocytes (calculate reticulocyte index (RI), RI = reticulocyte count x hematocrit (Hct)/normal Hct; a value of 45 is usually used for normal Hct) and peripheral blood smear should be performed. If any blood parameters remain clinically abnormal after 4 weeks of dose interruption, the patient should be referred to hematologist for further investigations. Bone marrow analysis and/or blood cytogenetic analysis should be considered at this stage according to standard hematological practice.
 - Development of a confirmed myelodysplastic syndrome or other clonal blood disorder should be reported as an SAE. Study treatment should be discontinued if diagnosis of myelodysplastic syndrome is confirmed.

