3.3.2.4 Anemia

- Symptomatic anemia should be treated with red blood cell transfusion and is recommended if the hemoglobin falls below 8 g/dL or the patient is symptomatic.

3.3.3 General Recommendations for Dose Modification and Management of Non-Hematologic Adverse Events

- The management of general AEs not otherwise specified in the following sections should be as per **Table 9**.
- At the discretion of the investigator, the study drugs may be held or dose modified independently if the observed toxicity is attributed to only one of the drugs, while the patient continued to receive the drug not associated with the observed toxicity.
- Dose modifications for nausea, vomiting, and diarrhea will be made only if they are refractory to treatment. The time a given drug is held should not exceed 21 days.

Table 9. General Management of Adverse Events (Non-Hematologic)

Observation	Action
Grade 1 or 2 AEs resolves promptly (within 48 hours) with supportive care	Maintain dose level (DL)
Any \geq grade 3 non-hematologic*	Hold study drug(s) causing the toxicity for up to 21 days until toxicity resolves to \leq grade 1. Treatment with olaparib or EP0057 may be restarted at one DL lower, as per the dose reduction guidelines.
Grade 3 or 4 non-hematologic AE related to drugs that does not resolve to grade 1 or less within 21 days despite maximum supportive care after treating patient at the lowest reduced DL	Remove patient from the drug causing the toxicity.
Toxicities requiring more than 2 dose reductions	Remove patient from the drug causing the toxicity.

*Except fatigue/asthenia < 2 weeks in duration; mucositis in subjects who have not received optimal therapy for mucositis; vomiting or diarrhea lasting less than 72 hours whether treated with an optimal anti-emetic or anti-diarrheal regimen or not; or alkaline phosphatase changes

- Management of new or worsening pulmonary symptoms

If new or worsening pulmonary symptoms (e.g. dyspnea) or radiological abnormality occurs, an interruption in olaparib dosing is recommended and a diagnostic workup (including a high resolution CT scan) should be performed, to exclude active pneumonitis. Following investigation, if no evidence of abnormality is observed on CT imaging and symptoms resolve, then olaparib treatment can be restarted, if deemed appropriate by the investigator.

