3.6.1 Criteria for Removal from Protocol Therapy

- Progressive disease
- Participant requests to be withdrawn from active therapy
- Unacceptable Toxicity as defined in Sections [3.1.1](#) and [3.3](#)
- Toxicity related dose delay lasting longer than 21 days in which case patient will be removed from the drug causing the toxicity.
- Investigator discretion
- Requirement for any of the prohibited study drugs as described in [Appendix B](#), Section [16.2](#) (Strong and moderate Inhibitors and Inducers of CYP3A)
- The subject becomes pregnant
- Active pneumonitis

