4.1.2 Palliative radiotherapy

Palliative radiotherapy may be used for the treatment of pain at the site of bony metastases that were present at baseline, provided the Investigator does not feel that these are indicative of clinical disease progression during the study period. Study treatment should be discontinued for a minimum of 3 days before the patient undergoes palliative radiation treatment. Study treatment should be restarted within 28 days from the scheduled date as long as any bone marrow toxicity has recovered.

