and beta = 0.20 (probability of rejecting a good treatment=0.20), this first stage will enroll 15 evaluable patients, and if 0 to 4 of the 15 have a success (that is, 0 to 4 make it to 16 weeks without progression), then no further patients will be accrued. If 5 or more of the first 15 patients have success, then accrual would continue until a total of 27 evaluable resistant/refractory patients have been enrolled. As it may take up to 4 months to determine if a patient has experienced a success at 16 weeks, a temporary pause in the accrual may be necessary to ensure that enrollment to the second stage is warranted. If there are 5 to 9 patients with a success out of 27 patients, this would be an uninterestingly low success rate. If there were 10 or more of 27 (37%) who experienced a success, this would be sufficiently interesting to warrant further study in later trials. Under the null hypothesis (25% success rate), the probability of early termination is 68.7%.

Patients who receive at least one dose of the study drug will be evaluable for safety. Patients who complete at least one cycle of treatment and have a follow up imaging study will be evaluable for efficacy. The maximum number of patients on the phase I portion of the trial is 30 and phase II SCLC may accrue up to 27 evaluable patients. Thus, the maximum number of evaluable patients which may enroll on the phase I and II cohorts is 57. In order to allow for a small number of in-evaluable patients, the accrual ceiling will be set at 60 for these cohorts. It is anticipated that approximately 1 to 2 patients per month may enroll onto these cohorts.

Table 15. Selected randomized studies of cytotoxic agents for SCLC

No.	Patients	Treatment s	Primary endpoint	Median PFS-topotecan	Median OS-topotecan	Reference
1	Sensitive SCLC	Topotecan (N=107) vs. CAV (N=104)	ORR	3.3 months (sensitive)	6.3 months (sensitive)	(68)
2	Refractory or sensitive SCLC; 2 nd line	Topotecan (N=213) vs. amrubicin (N=424)	OS	4.3 months (sensitive) 2.6 months (refractory)	9.9 months (sensitive) 5.7 months (refractory)	(71)
3	Sensitive SCLC 2:1	Topotecan (N=26) vs. amrubicin (N=50)	ORR	3.3 months (sensitive)	7.6 months (sensitive)	(73)
4	Refractory or sensitive SCLC	Topotecan (N=30) vs. amrubicin (N=29)	ORR	3.0 months (sensitive) 1.5 months (refractory)	NA	(70)
5	Sensitive SCLC; 2 nd line	PO (N=153) vs. IV	ORR	3.7 months (sensitive)	8.7 months (sensitive)	(72)

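### After an EP0057 delay of more than 21 days, Section 14.1.6 takes the patient off treatment, while Sections 3.3 and 3.6.1 remove only the drug causing the toxicity

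*Combined protocol and SAP*

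**What the plan says.** Five parts of the current protocol bear on a toxicity delay that outlasts 21 days.

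- **Section 14.1.6 (EP0057, Dosage and Administration).** The paragraph is about delaying the second and later EP0057 doses when related adverse events have not settled. It ends: "However, the maximum delay for AEs to resolve is 21 days beyond which the patient will be taken off treatment".
- **Section 3.6.1 (removal from protocol therapy).** The listed criterion is: "Toxicity related dose delay lasting longer than 21 days in which case patient will be removed from the drug causing the toxicity".
- **Section 3.3.2.1 (hematologic toxicity).** The general limit reads: "Treatment may be delayed for a maximum of 21 days after holding the treatment for toxicities". In Table 8, patients whose counts have not recovered "after 21 days should be removed from the drug causing the toxicity".
- **Table 9 (Section 3.3.3, non-hematologic toxicity).** For a grade 3 or 4 event still unresolved after 21 days at the lowest reduced dose level, the action is: "Remove patient from the drug causing the toxicity".
- **Section 3.3.2 (general rules).** "If either agent is discontinued due to toxicity, the patient may continue on the other agent".

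Single-agent treatment is also provided for elsewhere. Section 3.2.2 and footnote 11 of the Study Calendar (Section 3.4) let olaparib run without a break when EP0057 is missed, whatever the reason. Footnote 28 waives the day-15 assessments for patients on olaparib alone.

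**The concern.** Section 14.1.6 and the dose-modification and removal sections start from the same event, a toxicity delay longer than 21 days, and prescribe different actions. One is written as the end of treatment for the patient. The others end one drug and leave the second available. No order of precedence is stated. Section 14.1.6 refers the reader to Section 3.3, which contains the differing rule.

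What is at stake is first the handling of individual patients: whether someone whose toxicity is put down to one drug keeps the other. The question is live. Section 3.1 states that Phase I is complete and that accrual to the urothelial and mCRPC cohorts has ended, which leaves the SCLC cohort open. A second, weaker consequence is that patients with the same course could differ in exposure to study drug, and in the visits they attend, before the week-16 assessment.

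**Working it through.** The conflict is one of text, so the check is to follow one patient through each section.

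**Step 1. Same event, three attributions.** EP0057 is held for toxicity and the hold passes 21 days.

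| Toxicity attributed to | Section 14.1.6, read literally | Sections 3.6.1, 3.3.2, Table 8 (and Table 9 at the lowest dose level) | Conflict? |
|---|---|---|---|
| EP0057 only | Off treatment | Off EP0057; olaparib may continue | Yes |
| Olaparib only, EP0057 also delayed | Off treatment | Off olaparib; EP0057 may continue | Yes |
| Both drugs | Off treatment | Off both | No |

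The rules therefore diverge only when one drug is held responsible. Section 3.3.2 leaves that attribution to the principal or associate investigator.

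**Step 2. Can it happen before week 16?** Take the cycle 1 day 15 dose as an example. A delay of 21 days from day 15 reaches day 15 + 21 = 36. The first scheduled scan follows two 28-day cycles, at about day 2 × 28 = 56. Week 16 is day 16 × 7 = 112. So the two paths can separate before the first scan and well before the endpoint.

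**Step 3. Does the choice of rule decide who counts as a success?** Not directly. Section 6.3.7 counts progression or death as the event. Section 10.1 states the first-stage rule as "if 0 to 4 of the 15 have a success (that is, 0 to 4 make it to 16 weeks without progression". Stopping one drug or both is a failure under neither. A patient off all treatment and progression-free at week 16 is a success on the same terms as one still on a single agent.

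**Step 4. What indirect route remains?** There are two.

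- Exposure: one patient goes on receiving a drug and the other does not.
- Observation: a patient on one drug stays on the scan schedule of every two cycles. For a patient off treatment, the précis names survival follow-up every 3 months, and the calendar lists an end-of-treatment visit about 4 weeks after discontinuation and then a phone call. Against that, Section 3.1 ends tumor assessments at progression, not when treatment stops.

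**Step 5. Are the design figures affected?** The plan's own figures were reproduced with exact binomial sums.

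- Early termination under p0 = 0.25: the sum over x = 0 to 4 of C(15, x) × 0.25^x × 0.75^(15−x) = 0.6865, against the stated 68.7%.
- Probability of at least 10 of 27 successes after passing stage one: the sum over x = 5 to 15 of P(X1 = x) × P(X2 ≥ 10 − x), where X1 is binomial (15, p) and X2 is binomial (12, p). This gives 0.0973 at p = 0.25 (limit 0.10) and 0.8012 at p = 0.45 (target 0.80).

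None of these depends on the rule for stopping treatment, and none is wrong because of the conflict.

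**Step 6. Is there a frequency?** Section 1.2.16 reports one patient of 6 at dose level 4 who could not begin the next course within 28 days of the scheduled date because of neutropenia. A delay beyond 21 days has therefore occurred in this trial, but at a higher olaparib dose than the recommended Phase II dose. No rate is given for Phase II.

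**The case against.** The strongest reply is that the sentence sits in the EP0057 drug section and closes a paragraph solely about EP0057 doses, so being off treatment may simply mean off EP0057. The operative sections agree with one another, the drug section refers back to them, and olaparib alone is built into the dosing rules and the calendar. On this view few staff would be misled. This stands as a plausible account of intent. It does not settle the matter, because the sentence names EP0057 when it speaks of doses and then speaks of the patient and of treatment without that limit. Followed as written, it stops a patient whom the other sections allow to continue.

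Three stronger readings may tempt a reader, and the documents support none of them.

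- **That only the single-agent patient can count as a week-16 success.** Discontinuation is not an event in Section 6.3.7 or Section 10.1, so an off-treatment patient can count too.
- **That a known share of the 27 patients is affected.** A reader might carry the 1 of 6 dose-limiting toxicities at the recommended dose over to 27 patients (27 × 1/6 = 4.5), or take 1 to 5 patients, roughly 4 to 19 percentage points. That one event was grade 4 neutropenia not resolving within 7 days, not a delay over 21 days. Phase I also barred preventive growth factors during the toxicity window (Section 3.3.2.2), whereas Section 3.2.2 recommends them from cycle 1 in Phase II. A power loss computed from an assumed share of lost successes would likewise have no basis in the documents.
- **That Section 4.1.2 adds a third conflicting limit.** It says "Study treatment should be restarted within 28 days from the scheduled date", but the trigger is palliative radiotherapy for bone pain. A different trigger may have a different limit.

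**Conclusion.** The inconsistency holds, in current text. Beyond a 21-day toxicity delay of EP0057, Section 14.1.6 read literally ends all treatment, while Section 3.6.1, Table 8, Table 9 (at the lowest reduced dose level) and Section 3.3.2 end only the causative drug. It matters when toxicity is attributed to one drug and disappears when it is attributed to both.

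Its size is one of patient handling: stopped entirely or continued on the other drug. How many patients this touches cannot be derived from the documents. Any effect on the primary endpoint is indirect, through exposure and through whether a week-16 scan is obtained after treatment stops, and cannot be sized either. The conclusion rests on reading Section 14.1.6 as written. If off EP0057 was meant, the fault is one of wording, and it still needs correcting because the text does not say so.

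**What to change.** Reconcile Section 14.1.6 with Sections 3.2.2, 3.3.2 and 3.6.1, Tables 8 and 9, and calendar footnotes 11 and 28, so that a delay beyond 21 days leads to one stated action wherever it is described. State explicitly whether that action applies to the causative drug or to both drugs. Which rule applies is for the sponsor to decide. The 28-day limit after radiotherapy need not be part of this change.

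The cost is an amendment to wording. Sample size, decision boundaries and visits do not change.
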